## 7. **Patient Eligibility**

### a. **Study setting**

A monitored ward or ICU in which patients with confirmed or suspected COVID19 are receiving high flow nasal cannula

### b. **Study population**

Patients who have *suspected or confirmed* COVID19 who have infiltrates on CXR and who have an oxygen requirement of >4L to keep oxygen saturations about 94% using high flow nasal cannula

### c. **Eligibility criteria**

#### **Inclusion criteria**

Suspected or confirmed COVID19 infection  
Bilateral Infiltrates on CXR  
SpO2 <94% on FiO2 40% by high flow nasal cannula  
Able to provide written informed consent

#### **Exclusion criteria**

Age <18  
RR>40  
Uncooperative or likely to be unable to lie on abdomen for 16 hours  
Immediate need for intubation  
SBP<80  
Vomiting or bowel obstruction  
Palliative care  
Multiorgan failure  
Standard contraindications to prone positioning include the presence of an open abdominal wound, unstable pelvic fracture, spinal lesions and instability, pregnancy > 20/40 gestation and brain injury without monitoring of intracranial pressure.

### d. **Co-enrolment guidelines**

Patients will be eligible for inclusion in other studies

## **8. Patient screening, consent and recruitment**

### **a. Patient screening**

All patients admitted to a COVID19 ward, COVID ICU or HDU will be screened for inclusion in the study.

### **b. Informed consent procedure**

As patients will be self-ventilating, written informed consent or witnessed telephone consent to reduce fomite transmission will be obtained for each patient enrolled in the study. A patient information leaflet will be given to all patients screened as eligible. After a period of time to read and consider the information leaflet time will be given for questions, and then if the patient consents to be involved, written consent will be obtained. Due to the risk of fomite result of informed consent will be witnessed and recorded in the patient chart. The original consent form will be disposed of in yellow waste from the patient room, which should be destroyed.

## **9. Assignment of intervention**

Awake prone positioning will be performed before or 1 hour after meal. Call bell will be given to the patient and an oxygen probe will be attached to the patient to monitor spO2 during the procedure. Before PP, all the I.V. lines and nasal cannula will be checked by clinicians. Awake prone positioning will be performed by patient under the supervision of clinicians. Assistance will be offered if needed. If tolerated, PP will be maintained for at least 30 minutes, until the patients feel tired to keep that position. Patients will be informed to maintain prone position as long as they can. FIO2 will be adjusted to maintain SpO2 at 92-95%. Protocol for sedation and comfort evaluation during PP: No sedation will be used during the PP on ward. The patients are monitored by bedside respiratory therapist and nurses for their comfort and tolerance for the PP at 5mins, 30 minutes after PP for the first PP in each day.

### **a. Withdrawal criteria**

- Patients cannot tolerate HFNC or prone position for 30 mins
- Patients experience any side effects during prone position, including vomit, dizzy, hypotension, etc.

### **b. Weaning criteria**

- Patients' PaO2/FIO2 > 300, or SpO2/FIO2 > 340

### **c. Treatment Failure Criteria**

Failure criteria: treatment failure is defined as one of the following criteria:

- Signs of persisting or worsening respiratory failure, defined by at least two of the following criteria:
  - Respiratory rate above 40 cycles/min
  - Lack of improvement of signs of respiratory-muscle fatigue
- -Development of copious tracheal secretions
- -Respiratory acidosis with a pH below 7.35
- -SpO2 below 90% at FIO2 ≥ 0.8 for more than 5 min without technical dysfunction

- Hemodynamic instability defined by a SBP below 90 mmHg, MBP below 65 mmHg or requirement for vasopressor;
- Deterioration of neurologic status (with AVPU to pain). For patients who meet the failure criteria in the standard treatment and PP groups, a trial of NIV will be allowed according to the physician's preference in patients with signs of persisting or worsening respiratory failure and no other organ dysfunction before performing endotracheal intubation and invasive ventilation. Reasons for intubation will be recorded as well.

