#### ***b. Analysis population***

Data will be analysed on an intention to treat basis with all data for patients who consented to be involved included in baseline data analysis. Outcome data will be analysed for all patients who were positioned in the prone position for any length of time. A further per protocol analysis will be carried out on all patients who tolerated at least 1 hour of the daytime proning time and at least 2 hours of the night time proning period in any 24 hour period. Patients who were rescue prone will be considered a protocol deviation and will be studied as a group. Definition of the two groups: The

patients who receive the prone positioning are classified as prone positioning group. The patients who receive HFNC alone are classified as HFNC group. Comparisons between the two groups: Quantitative continuous variables are given as either means ( $\pm$ SDs) or medians (with inter-quartile ranges) are compared using the unpaired Student's t test or the Mann-Whitney test. Qualitative or categorical variables are compared with the chi square test or the Fisher's exact test. ANOVA for paired tests to compare the same variables collected at different time points are used. The cumulative probability of remaining on spontaneous breathing are compared with the Kaplan-Meier estimate of survival and the log-rank test to compare the two groups. Univariate and multivariate analyses of risk factors for PP failure are performed with logistic regression. All analyses are in intention to treat, and the level of significance is set at 0.05.

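### An eligible patient with systolic pressure of 80–89 mmHg already meets the written treatment-failure definition at entry; mean pressure and vasopressor need leave the same gap

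*Combined protocol and SAP*

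**What the plan says.** **Eligibility (section 7c).** The inclusion list covers infection, infiltrates, oxygenation and consent, and gives no blood-pressure limit. The exclusion list removes patients with systolic pressure below 80 (no unit is printed; mmHg is assumed here). It does not mention mean pressure or vasopressors. Two other exclusions could remove some hypotensive patients: "Immediate need for intubation" and "Multiorgan failure". Neither is defined by blood pressure.

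**Failure (section 9c).** The rule is that "treatment failure is defined as one of the following criteria". One stand-alone item is "Hemodynamic instability defined by a SBP below 90 mmHg, MBP below 65 mmHg or requirement for vasopressor". It does not require the finding to be new, sustained or changed from baseline. The definition covers both arms: "For patients who meet the failure criteria in the standard treatment and PP groups", a trial of non-invasive ventilation is allowed at the physician's preference before intubation. That option is limited to patients with respiratory signs and no other organ dysfunction.

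**Withdrawal (section 9a).** Hypotension during prone positioning is a withdrawal criterion, with no threshold.

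**Analysis.** The primary outcome (section 6a) is invasive ventilation or death by 28 days. Treatment failure is not among the secondary outcomes (section 6b). Section 11b plans that "Univariate and multivariate analyses of risk factors for PP failure are performed with logistic regression", without defining PP failure or the candidate factors.

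**The concern.** Entry and failure are judged on the same measurement with different limits, and the failure limit is the less extreme one. A patient can therefore satisfy a failure criterion before allocation has had any effect. A patient who enters at 85 mmHg and stays there meets the definition throughout without deteriorating.

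Two things are at stake. First, section 9c is the passage that leads towards escalation, and intubation counts as a primary event. Whether a pressure that was already low at entry should prompt escalation is left to staff who know the allocation (section 9e). Second, if the regression in section 11b takes its outcome from section 9c, a baseline pressure below 90 mmHg is part of the outcome it would be said to predict.

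**Working it through.** **1. The two rules side by side**

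| Measure | Exclusion (7c) | Failure (9c) | Eligible and already meeting failure |
|---|---|---|---|
| Systolic pressure | below 80 | below 90 mmHg, sufficient alone | 80 to below 90 mmHg |
| Mean pressure | none | below 65 mmHg, sufficient alone | any value below 65 mmHg, if not otherwise excluded |
| Vasopressor | none | requirement, sufficient alone | any patient requiring one, if not otherwise excluded |
| Respiratory rate | above 40 | above 40, and a second sign is needed | none |

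For systolic pressure, {80 or above} ∩ {below 90} = {80 to below 90}, a band of 90 − 80 = 10 mmHg. For respiratory rate the failure item is "Respiratory rate above 40 cycles/min", the same limit as the exclusion, so there is no overlap. The two lists were aligned on that measure and not on the haemodynamic ones.

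**2. Does another passage close the gap?** No section says from when failure is assessed, or that values present at randomisation do not count. The exclusions for imminent intubation and multiorgan failure narrow the group but do not empty it by definition.

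**3. Where the failure definition is used.** It is not used in the primary or listed secondary outcomes. It bears on escalation in section 9c. It bears on the section 11b regression only if PP failure there means the section 9c criteria. That term could also mean intubation, or failure to tolerate the position (section 9a).

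**4. Size**

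The plan's own figure comes first. Inputs from section 11a are 60% against 40%, alpha 0.05 and beta 0.2. The usual two-sided formula with pooled variance under the null and no continuity correction is

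n = [z(0.975)·√(2·p̄(1−p̄)) + z(0.80)·√(p1(1−p1) + p2(1−p2))]² / (p1−p2)²

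With p̄ = 0.5 this is (1.960·√0.50 + 0.842·√0.48)² / 0.04, which rounds up to 97 per arm, as stated. The planned 196 patients give 98 per arm and 80.4% power.

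The documents do not give the share of patients in the overlap. As an illustration only, assume that a share q of each arm is intubated because of a criterion present at entry, whatever the allocation, and that the rest follow 60% and 40%. The arm rates are q + (1−q)·0.60 and q + (1−q)·0.40, so the difference shrinks to 0.20·(1−q).

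| q (assumed) | Control | Prone | Difference | n per arm for 80% | Power at 98 per arm |
|---|---|---|---|---|---|
| 0% | 60.0% | 40.0% | 20.0 points | 97 | 80.4% |
| 2% | 60.8% | 41.2% | 19.6 points | 101 | 78.8% |
| 5% | 62.0% | 43.0% | 19.0 points | 108 | 76.3% |
| 10% | 64.0% | 46.0% | 18.0 points | 119 | 72.0% |

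For a given share of patients in the overlap this is the extreme case, because every one of them is assumed to be intubated. It also adds them on top of the planned 60%, although that rate was proposed for the cohort as defined and may already include them.

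**The case against.** The case for setting the point aside is as follows.

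- **Failure is not an outcome.** This stands. No listed endpoint counts a section 9c criterion, so a reader who infers that a trial result is recorded as failed at time zero goes beyond the documents.
- **Section 9c does not order intubation.** This also stands. It allows non-invasive ventilation in some patients and asks for the reasons for intubation. Haemodynamic failure may fall outside the non-invasive option, but no section says that a stable patient at 85 mmHg is to be intubated.
- **Failure of treatment is naturally judged after treatment starts**, and neighbouring items speak of persistence, worsening, development or deterioration. This partly stands: it makes failure at entry a literal reading of the rule rather than a certain classification. It does not repair the haemodynamic item, which has no such wording and which an unchanged low pressure meets at any later time.
- **The rule is the same in both arms of a 1:1 randomised trial.** This stands. Affected patients should be balanced in expectation, and no directional bias is shown. Open-label judgement could add some, but the documents do not establish it.
- **The link to the regression is inferred.** This stands as a condition. Even where it holds, the effect is on a risk-factor analysis and not on the comparison of the arms.
- **Hypotension while prone is addressed in section 9a.** This is true, and the exclusion list governs entry to both arms rather than declaring a pressure acceptable for proning. A direct patient-safety contradiction is therefore more than the text supports. Section 9a gives no threshold, so it does not remove the overlap.

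**Conclusion.** The inconsistency is established from the text alone: a patient with systolic pressure of 80 to below 90 mmHg is not excluded on pressure and meets the written failure definition at entry. The same can occur through mean pressure or vasopressor need.

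Its consequences are limited. The number of patients is unknown and may be small. The expected effect is misclassification against the section 9c definition and, to the extent that it prompts intubation, some dilution of the treatment difference. Under the undocumented assumptions above, power would fall from 80.4% to between 78.8% (q = 2%) and 72.0% (q = 10%); these figures show scale and are not estimates. The effect on the regression depends on PP failure meaning the section 9c criteria.

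A reader might infer that every such patient is certain to be misclassified, or that the primary result is biased towards one arm. The documents support neither. The point is worth acting on because the written rules conflict and the correction is cheap, not because it threatens the trial's main conclusion.

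**What to change.** 1. Reconcile the haemodynamic criteria in sections 7c and 9c for systolic pressure, mean pressure and vasopressor requirement together, and the hypotension withdrawal criterion in section 9a with them. Correcting systolic pressure alone would leave the other two gaps open. How they are reconciled is for the clinical investigators; no view is taken here on which limit is right.
2. In section 11b, define PP failure, and state whether it refers to the section 9c criteria, to intubation or to intolerance of the position.
3. For that analysis, state how criteria already present at randomisation are handled, so that a baseline value is not counted as an outcome. This is an analysis rule and need not change bedside management.

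The cost is a short amendment and possibly a very small change in the eligible pool. The sample size calculation does not need to change on this account.

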#### ***d. Allocation and Randomisation***

Within 6 hr of fulfilling inclusion criteria, a patient will be randomly allocated either to the prone positioning group or the control group (HFNC alone with no prone positioning therapy). Patients will be randomly allocated to either arm of the study at a ratio based on a 1:1 basis using a REDCAP randomisation process. Randomization will be stratified by site using tables of random permutations using the RECAP database for randomization. The random block length is 4, and random numbers are generated by computer.

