#### **5. Study Details**

##### **a. Study design**

Multi centre open label randomized controlled study in which patients are randomized to awake prone positioning or standard care. This trial is registered with ClinicalTrials.gov (NCT04347941). This trial is part of a prospective meta-trial listed in appendix 1.

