#### ***e. Blinding***

It is not feasible to blind staff or patients as to the procedure. Study data will be blinded for the purposes of analyses, assigned as group 1 or group2 rather than prone / not prone.

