**b. *Protocol compliance***

A Request for sponsorship from the CRFG at NUI Galway has been sought which will provide the necessary manpower for trial oversight, quality, statistical analysis. Online training on study protocol will be conducted prior to site initiation. Investigators will be available for any data entry queries or clinical concerns.

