### ***14. Dissemination***

Results of both registry and randomised controlled trial will be published in an international journal following peer review. To incentivise participation in the study, centres that recruit a patient will be permitted to have one author on final publication. For each additional 10 patients recruited, a further author from that centre will be added to the authors list.

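### A single block length of 4 within site, stated in the protocol of an open-label trial, makes up to one in three allocations predictable with certainty

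*Combined protocol and SAP*

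**What the plan says.** Section 9d describes allocation through REDCap at 1:1. "Randomization will be stratified by site", and the next sentence reads "The random block length is 4, and random numbers are generated by computer". No second length and no random choice between lengths is mentioned, so the word random there cannot mean that the length varies. Site is the only stratification factor named, so each site runs one sequence of blocks of 4, with two prone and two control patients in each complete block.

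Section 5a calls the trial a "Multi centre open label randomized controlled study", and Section 9e adds "It is not feasible to blind staff or patients as to the procedure". Masking covers only the group labels in the analysis data. Section 13b says "Online training on study protocol will be conducted prior to site initiation". The text does not say that the block length is withheld from recruiting staff.

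**The concern.** Central allocation hides the list, but not a pattern that follows from a known constant length. In an open-label trial the earlier allocations at a site are visible, so the end of each block can be worked out.

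Foreknowledge matters only if recruiters have some discretion, and they have some here. One exclusion in Section 7c is a judgement: "Uncooperative or likely to be unable to lie on abdomen for 16 hours". Immediate need for intubation is another, and it bears directly on the primary outcome. A consent conversation also comes before enrolment (Section 8b). Section 3c records that the investigators have already seen improvement with proning, so a preference between arms is conceivable, even an unconscious one.

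If patients at lower risk were enrolled more readily when the next slot was known to be prone, the arms would differ in baseline risk. Intention-to-treat analysis does not correct selection that occurs before randomisation, and the between-group tests in Section 11b are unadjusted.

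**Working it through.** **The plan's own figure.** Section 11a gives event rates of 60% and 40%, alpha 0.05 and beta 0.2. Taking the test as two-sided (the plan does not say), with pooled variance and no continuity correction:

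n = [1.960 × √(2 × 0.5 × 0.5) + 0.842 × √(0.24 + 0.24)]² / 0.20² = 96.9, that is 97 per group.

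This agrees with the plan. It does not depend on block length, so the point concerns selection bias and not power. The plan gives no figure for predictability. Its total of 196 means 98 per arm, which is used below.

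**Certain slots in a block of 4.** There are 6 equally likely orders of two prone and two control. A slot is certain when one arm is already used up in the block.

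| Slot | Probability certain | Best-guess success |
|---|---|---|
| 1 | 0 | 0.500 |
| 2 | 0 | 0.667 |
| 3 | 1/3 | 0.667 |
| 4 | 1 | 1.000 |
| Mean | 0.333 | 0.708 |

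The best guess is always the arm that is behind in the block.

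**By patients at a site.** The expected certain share is the mean of the slot probabilities over the first n patients. For n = 10 it is (4/3 + 4/3 + 0 + 0)/10 = 26.7%.

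| Patients at site | 1–2 | 3 | 4 | 5 | 6 | 7 | 8 | 10 | 12 or 20 |
|---|---|---|---|---|---|---|---|---|---|
| Certain | 0% | 11.1% | 33.3% | 26.7% | 22.2% | 23.8% | 33.3% | 26.7% | 33.3% |

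One third is therefore the ceiling of the expected share. The documents do not give patients per site. Section 14 allows for very small ones: "centres that recruit a patient will be permitted to have one author on final publication".

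**Illustration of the consequence.** These are assumptions, not figures from the plan: no true effect, base risk 60%, 98 per arm, and enrolled risk lower by d when the next slot is known to be prone and higher by d when it is known to be control. Then

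spurious benefit = 2d × certain share × fraction of certain slots exploited.

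The standard error of the difference is √(2 × 0.6 × 0.4 / 98) = 0.070. Type I error is two-sided at 0.05 by normal approximation. With d = 10 points:

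| Fraction exploited | Complete blocks (33.3%) | 10 patients per site (26.7%) |
|---|---|---|
| One quarter | 1.7 points, 5.7% | 1.3 points, 5.4% |
| One half | 3.3 points, 7.6% | 2.7 points, 6.7% |
| All | 6.7 points, 16% | 5.3 points, 12% |

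Bias depends only on the product of d and the fraction exploited, so smaller shifts can be read from the same table. Over complete blocks with full exploitation, d = 5 points gives 3.3 points and 7.6%; d = 2 points gives 1.3 points and about 5.4%.

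**Varying lengths 4, 6 and 8.** This was simulated with equal probabilities, for an observer who knows the set of lengths and the site's full history. At 20 patients per site:

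| | Fixed 4 | 4/6/8 |
|---|---|---|
| Certain slots | 33.3% | 2.4% |
| Type I error, all certain slots exploited (d = 10) | 16% | 5.1% |
| Best-guess success | 70.8% | 67.2% |
| Every best guess acted on (d = 10) | 8.3 points, 22% | 6.9 points, 17% |

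The last row uses 2d × (2 × success − 1): 0.20 × 0.417 = 8.3 points and 0.20 × 0.344 = 6.9 points.

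**The case against.** The arithmetic is not in dispute; its weight is. Section 9d requires allocation within 6 hours of a patient meeting the inclusion criteria, which limits holding a patient back for a preferred slot. Section 8a has every admission to the COVID units screened, and many criteria are objective. Section 14 rewards further recruitment with authorship, which discourages turning eligible patients away. Recruitment spans ward, HDU and ICU, so certainty requires someone to follow every allocation across units and know where each block starts. Training on the protocol need not mean that recruiters learn or use the block length. The 10-point shift has no source in the documents. Against staff who act on guesses, varying lengths help only a little.

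Most of this stands as a limit on exploitation. It makes a large bias less likely, and the 16% and 22% figures are extremes that should not be read as expected values. None of it prevents the deduction: the length is in the protocol, past allocations are visible, and judgement-based exclusions and consent come before randomisation. The missing source for the shift is handled by reading the illustration over a range, down to about 5.4%. The small gain against guessing is real and should be stated alongside the change.

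**Conclusion.** The concern holds. With one block length of 4 within site, up to one third of allocations can be known in advance by staff who know the length and track their site's sequence. The share is exact by enumeration, reached over complete blocks, and lower where the last block at a site is incomplete. That prediction is possible follows from the documents. That it would be used does not, and the bias and type I error figures rest on the assumed risk shift and fraction exploited. Fixed blocks of 4 remain valid randomisation and no stated sample-size figure changes. This is an avoidable weakness in allocation concealment that should be corrected because the remedy is cheap.

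**What to change.** For all blocks not yet opened, regenerate the REDCap allocation tables with randomly varying block lengths within site, for example 4, 6 and 8. Replace the block-length sentence in Section 9d with:

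> Allocation is 1:1, stratified by site, in computer-generated permuted blocks of randomly varying length; the lengths are held in a restricted randomisation document not available to recruiting staff.

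The direct cost is one new table and one sentence. The sponsor should also check whether the change needs notice to the ethics committees named in Section 13a or to the meta-trial group (Section 5a); the documents do not say. The largest possible imbalance between arms within a site rises from 2 to 4 patients, which matters mainly at small sites. Certainty is nearly removed, but a best guess would still be right about two times in three. Withholding the lengths should lower that further; this was not quantified.
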